terminal-phase half-life is 0.132 mL/h/kg, 81.2 mL/kg, and 22.1 days, respectively. These values are consistent with those of natural IgG2.

The profile of AEs and the spectrum of event severity have remained stable across the tremelimumab clinical program and are consistent with the pharmacology of the target. To date, no tumor type or stage appears to be associated with unique AEs (except for vitiligo that seems to be confined to subjects with melanoma). As of the data cutoff date of 30Aug2013, events reported in the tremelimumab monotherapy studies at a frequency > 5% and assessed by the investigator as treatment related were diarrhea (41.2%), rash (27.2%), pruritus (25.1%), fatigue (23.8%), nausea (21.9%), vomiting (13.5%), decreased appetite (11.3%), headache (7.2%), pyrexia (7.0%), abdominal pain (6.7%), and colitis (5.5%). The events of diarrhea, rash, and pruritus are considered as identified risks. Infusion-related side effects are rare. Acute renal failure was reported in subjects who received the combination of tremelimumab and sunitinib in a Phase 1 study; however, acute renal failure has not been an expected AE for single-agent tremelimumab. The incidence and/or severity of many of the AEs observed following administration of tremelimumab can be reduced by adherence to current immune-related toxicity management guidelines.

At present, tremelimumab has been administered as mono- or combination therapy with other anti-cancer agents to more than 1500 patients as part of ongoing studies. Section _ contains details on the safety profile of tremelimumab monotherapy. Further information on tremelimumab safety, efficacy and pharmacokinetics is provided in the Investigator Brochure.

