2.3.5 Potential Risks of Durvalumab + Tremelimumab in the Relevant Indication

Overall risks

Monoclonal antibodies may target several immune checkpoint proteins. These include programmed cell death ligand 1 (PD-L1), programmed cell death-1 (PD-1) or cytotoxic T-lymphocyte antigen-4 (CTLA-4). The anticipated result is an enhanced endogenous immune responses directed against tumor cells. However, there is the likelihood for adverse effects on other tissues as a consequence of stimulating the immune system.

Adverse drug reactions most seen with the immune checkpoint inhibitor class of agents are likely an outcome of the effects of inflammatory cells on specific tissues. These are generally events with a potential inflammatory or immune mediated mechanism and which may require more frequent monitoring and/or unique interventions such as immunosuppressants and/or endocrine therapy. Almost any organ system is susceptible to these immune mediated effects, and are most commonly seen as gastrointestinal AEs such as colitis and diarrhoea, pneumonitis/interstitial lung disease (ILD), hepatic AEs such as hepatitis and liver enzyme elevations, skin events such as rash and dermatitis and endocrinopathies including hypo- and hyper-thyroidism.

Durvalumab

The following are some risks associated with durvalumab: diarrhea/colitis and intestinal perforation, pneumonitis/ILD, endocrinopathies (hypo- and hyper-thyroidism, type I diabetes mellitus, hypophysitis and adrenal insufficiency) hepatitis/increases in transaminases, nephritis/increases in creatinine, pancreatitis/increases in amylase and lipase, rash/pruritus/dermatitis, myocarditis, myositis/polymyositis, other rare or less frequent inflammatory events including neurotoxicities, infusion-related reactions, hypersensitivity reactions and infections/serious infections.

Please refer to the current version of the durvalumab IB for information on all identified and potential risks with the drug.

In monotherapy clinical studies AEs (all grades) reported very commonly ($\geq 10\%$ of patients) are fatigue, nausea, decreased appetite, dyspnea, cough, constipation, diarrhea, vomiting, back pain, pyrexia, asthenia, anemia, arthralgia, peripheral edema, headache, rash, and pruritus. Approximately 9% of patients experienced an AE that resulted in permanent discontinuation of durvalumab and approximately 6% of patients experienced an SAE that was considered to be related to durvalumab by the study investigator.

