The majority of treatment-related AEs were manageable with dose delays, symptomatic treatment, and in the case of events suspected to have an immune basis, the use of established treatment guidelines for immune-mediated toxicity (please see Section 7.7).

A detailed summary of durvalumab monotherapy AE data can be found in the current version of the durvalumab IB.

Tremelimumab

The following are some risks associated with tremelimumab monotherapy: GI effects (colitis, diarrhoea, enterocolitis and intestinal perforation), endocrine disorders (hypo and hyperthyroidism, hypophysitis and adrenal insufficiency), skin effects (rash, and pruritus), elevations in lipase and amylase and clinical manifestations of pancreatitis, other gastrointestinal events e.g. ulcerative colitis, dehydration, nausea and vomiting; hepatic events including hepatitis, and liver enzyme elevations; pneumonitis and ILD; nervous system events including encephalitis, peripheral motor and sensory neuropathies, Guillain-Barre and proximal muscle weakness; cytopenias including thrombocytopenia, anemia and neutropenia; infusion-related reactions, anaphylaxis, and allergic reactions; renal events including renal failure, acute kidney injury, nephritis, nephrotic syndrome, autoimmune nephritis and electrolyte abnormalities such as hypokalemia; autoimmune diseases including autoimmune arthritis, Sjogren's syndrome and giant cell temporal arteritis; hyperglycemia and diabetes mellitus; and pyrexia.

Please refer to the current version of the tremelimumab IB for information on all identified and potential risks with the drug.

Using pooled data from monotherapy clinical studies AEs (all grades) reported very commonly ($\geq 10\%$ of patients) were diarrhea, nausea, fatigue, pruritus, decreased appetite, rash, vomiting, dyspnea, constipation, cough, pyrexia, abdominal pain, decreased weight, headache, asthenia, and anemia. Approximately 16% of patients experienced an AE that resulted in permanent discontinuation of tremelimumab and approximately 45% of patients experienced an SAE.

Further information on these risks can be found in the current version of the tremelimumab IB.

A detailed summary of tremelimumab monotherapy AE data can be found in the current version of the tremelimumab IB.

Durvalumab + tremelimumab

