The safety of durvalumab + tremelimumab combination therapy was initially evaluated in the ongoing dose escalation and dose expansion Study 006, in patients with NSCLC, and is being studied in a number of other ongoing clinical trials, in a number of different indications, and has to date shown a manageable safety and tolerability profile.

The types of risks with the combination of durvalumab + tremelimumab (based on an equivalent durvalumab dose of 20m/kg and a tremelimumab dose of 1mg/kg) are similar to those for durvalumab and tremelimumab monotherapy. Emerging data from study 006, other studies evaluating the combination, and from combinations of other agents in the same class indicate an increased frequency and/or severity of some of these immune-mediated toxicities.

For information on all identified and potential risks with the durvalumab+tremelimumab combination please always refer to the current version of the durvalumab IB.

In durvalumab+tremelimumab combination studies at the dose of durvalumab 20mg/kg and tremelimumab 1mg/kg AEs (all grades) reported very commonly ($\geq 10\%$ of patients) are fatigue, diarrhea, nausea, dyspnea, decreased appetite, pruritus, vomiting, anemia, constipation, cough, abdominal pain, pyrexia, back pain, arthralgia, hypothyroidism, asthenia, oedema peripheral, weight, decreased hyponatraemia and rash.

Approximately 15% of patients experienced an AE that resulted in permanent discontinuation of study drug and approximately 15% of patients experienced an SAE that was considered to be related to durvalumab and tremelimumab by the study investigator.

A detailed summary of durvalumab + tremelimumab combination AE data can be found in the current version of the durvalumab IB.

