5. TREATMENT PLAN

5.1 Study Design and Duration

This study is an open-label, single center trial assessing the safety and feasibility of using perioperative neoadjuvant and adjuvant immune-therapy for resectable liver or lung metastases.

Cohort A will consist of neoadjuvant tremelimumab 75 mg IV flat dose and durvalumab 1500 mg IV flat dose. Adjuvant therapy will consist of 4 monthly doses of durvalumab 1500mg IV.

Cohort B will consist of neoadjuvant oleclumab 3000 mg IV flat dose followed by durvalumab 1500 mg IV flat dose. Adjuvant therapy will consist of 4 months of oleclumab every two weeks at 3000 mg IV flat dose and durvalumab every 4 weeks at 1500 mg IV flat dose. On days oleclumab and durvalumab are both administered, oleclumab will be given first (see Section 8.1.4).

Cohort C will consist of neoadjuvant durvalumab 1500 mg IV flat dose then Monalizumab 750mg IV flat dose. Adjuvant therapy will consist of 4 months of durvalumab 1500 mg IV flat dose and monolizumab 750 mg, both administered every four weeks.

[figure not shown]
Cohort A has been enrolling since the study initiation and will enroll up to 25 patients. At the time of amendment activation initially opening, cohort B may enroll 5 patients followed by 5 patient enrollment for cohort C. Enrollment will continue in this alternating manner with approximately 5 patient blocks at a time for these cohorts. Enrollment may be adjusted based on Medimmune/MD Anderson determined priorities and drug availability. Cohort B and C will each be 15 patients.

[figure not shown]

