10. STUDY CALENDAR AND SCHEDULES

Table 10.1 Study Calendar from Enrollment until Surgical Resection

TIME PERIOD	Screening	Wk	Wk	Comment
		1	4**	
	within 14 days	+/-3d	3 - 10 weeks**	
PROCEDURE				
Cohort A: Tremelimumab + Durvalumab		X		
Cohort B: Durvalumab + Oleclumab		X		
Cohort C: Durvalumab + Monalizumab		X		
Liver/lung resection			X	
Clinic Visit	X	X	X	
Physical Examination	X	X	X	
Vital Signs	X	X	X	Including BP, HR, temperature. Obtain vital signs
Review of Concomitant Medication	X	X	X	
Laboratory	X	X	X	CBC w/differential and platelet count, LFTs (ALT, AST, total bilirubin, alkaline phosphatase), BUN or serum urea level, creatinine, Ca, Mg, Na, K, Cl, glucose)
CEA lab		X	X	
HIV and hepatitis and PT/PTT	X (within 30 days allowed)			HIV, hepatitis B and C testing and PT/PTT
Specialized laboratory tests	X		X	Lipase, amylase, TSH, FT4
Pregnancy test (WOCBP only)	X	X		Serum or urine pregnancy test to be done within 72 hours prior to first dose.
ECOG PS	X	X	X	see appendix 1
Adverse Events Assessment	X		X	Per CTCAE v4.03 for Cohort A and v5.0 for Cohorts B and C
CT C/A/P with IV contrast with tumor measurements	X (within 30 days)		X	
Immunogenicity Assessment (special lab)		X	X	
Liver biopsy (tumor)	X			
Immuno- genicity Assessments, Peripheral Blood		12 red top tubes of blood with 5ml each will be collected for immunological assessment. See section 5.1.3 (up to 4 missed blood draws are allowed)		
**Factoring the occurrence of potential immune mediated adverse events prior to resection, an allowance of 3 - 10 weeks after the administration of neoadjuvant therapy will be permitted to complete metastatic and/or primary resection.				

CEA: Carcinoembryonic Antigen; ECOG PS: Eastern Cooperative Oncology Group Performance Status; TSH: Thyroid stimulating hormone; FT4: Free T4; WOCBP: Women of child bearing potential; CT C/A/P: CT scan chest, abdomen and pelvis

Table 10.2 Post-Resection Study Calender for Cohort A (Durvalumab + Tremelimumab)

(Week 1 begins the day Durvalumab treatment is given)

TIME PERIOD	Post-operative evaluation	Wk	Wk	Wk	Wk	Wk	Comment
		1	5	9	13	every 4months	
	(0.5-2wks post surgery)	+/-3d	+/-7d	+/-7d	+/-7d	+/-6 weeks	
PROCEDURE							
Durvalumab		X	X	X	X		If patient requires >12 weeks for postop recovery, they will not be initiated on adjuvant immunotherapy
Clinic Visit	X	X	X	X	X	X	
Physical Examination	X	X	X	X	X	X	
Vital Signs	X	X	X	X	X	X	Including BP, HR, temperature
Review of Concomitant Medication	X	X	X	X	X		

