Laboratory	X	X	X	X	X	X	CBC w/differential and platelet count, LFTs (ALT, AST, total bilirubin, alkaline phosphatase), BUN or serum urea level, creatinine, Ca, Mg, Na, K, Cl, glucose)
CEA	X			X		X	
TSH/FT4	X			X			
Lipase/amylase	X						
Immunogenicity Assessments, Peripheral Blood	X				X	X (at first visit only)	

Pregnancy test (WOCBP only)		X	As indicated clinically						Serum or urine pregnancy test to be done within 72 hours of dose				
ECOG PS	X	X	X	X	X			see appendix 1					
Adverse Events Assessment	X	X	X	X	X			Per CTCAE v4.03 for Cohort A and v5.0 for Cohorts B and C					
CT C/A/P with IV contrast with tumor measurements					X	X							
Immunogenicity Assessments, Peripheral Blood	Up to 12 tubes of blood with 5ml each will be collected for immunological assessment. For specific details see laboratory manual (up to 4 missed blood draws are allowed)												
	
CEA: Carcioembryonic Antigen; ECOG PS: Eastern Cooperative Oncology Group Performance Status; TSH: Thyroid stimulating hormone; FT4: Free T4; WOCBP: Women of child bearing potential; CT C/A/P: CT scan chest, abdomen and pelvis
 
Toxicity 30 day f/u can happen 30 days (+/- 2 weeks) after last treatment dose and this can be done by phone call.
 
Note after one year of follow-up without recurrence schedule of follow-ups can be adjusted according to standard of care. This will take precedence over the study calendar.
												

Table 10.3 Post-Resection Study Calender for Cohorts (B and C)

TIME PERIOD	Post-operative evaluation	Wk	Wk	Comment							
	1 (same day as Durvalumab)	3	5	7	9	11	13	15	every 4 months		
	(0.5-2wks post surgery)	+/-3d	+/-6 weeks								
PROCEDURE											
Durvalumab		X		X		X		X			
Oleclumab (cohort B)		X	X	X	X	X	X	X			If patient requires >12 weeks for postop recovery, they will not be initiated on adjuvant immunotherapy
Monalizumab (cohort C)		X		X		X		X			
Clinic Visit		X	X	X	X	X	X	X	X		
Physical Examination		X	X	X	X	X	X	X	X		
Vital Signs		X	X	X	X	X	X	X	X		Including BP, HR,

										temperature
Review of Concomitant Medication		X	X	X	X	X	X	X	X	
Laboratory		X	X	X	X	X	X	X	X	CBC w/differential and platelet count, LFTs (ALT, AST, total bilirubin, alkaline phosphatase), BUN or serum urea level, creatinine, Ca, Mg, Na, K, Cl, glucose)
CEA	X								X	X
TSH/FT4	X			X		X		X		
Lipase/amylase	X									
Immunogenicity Assessments, Peripheral Blood	X			X				X		X (at first visit only)

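### During adjuvant durvalumab, Cohort A has one scheduled TSH/FT4 test against three in Cohorts B and C, with no stated reason; adding Weeks 5 and 13 on blood already drawn would be a minor, cheap improvement

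*Combined protocol and SAP*

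**What the plan says.** Section 10 of the combined protocol and SAP has separate post-resection calendars: "Table 10.2 Post-Resection Study Calender for Cohort A (Durvalumab + Tremelimumab") and "Table 10.3 Post-Resection Study Calender for Cohorts (B and C"). Section 5.1.3 refers to them without explaining where they differ.

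For Cohort A, section 5.1 states: "Adjuvant therapy will consist of 4 monthly doses of durvalumab 1500mg IV". For Cohort B it states: "Adjuvant therapy will consist of 4 months of oleclumab every two weeks at 3000 mg IV flat dose and durvalumab every 4 weeks". Cohort C adds monalizumab every four weeks. Tremelimumab is given once, before surgery.

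The scheduled thyroid tests are:

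| Time point | Cohort A | Cohorts B and C |
|---|---|---|
| Screening and before surgery (Table 10.1) | yes | yes |
| Post-operative evaluation | yes | yes |
| Week 5 | no | yes |
| Week 9 | yes | yes |
| Week 13 | no | yes |
| Four-monthly follow-up | no | no |

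The routine laboratory draw in Table 10.2 is marked at Weeks 1, 5, 9 and 13, but its panel does not include TSH or FT4.

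Section 2.3.5 names hypo- and hyperthyroidism among the risks of durvalumab, and section 7.3 lists both as adverse events of special interest. Table 7.7.1, which applies to all cohorts, directs further work-up when TSH is markedly abnormal or stays out of range on two successive measurements.

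**The concern.** The durvalumab dose and weeks are the same in all cohorts, yet scheduled thyroid testing in Cohort A is one third of that in the other two. An onset soon after the first adjuvant dose may be recognised four weeks later in Cohort A. An abnormal Week 9 result has no scheduled repeat, although another dose follows at Week 13 and the protocol's own guidance uses repeated TSH values. An onset between Weeks 9 and 13 has no scheduled test at all.

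Two things are at stake: somewhat later recognition in individual patients, and descriptive thyroid event rates that come from unequal testing. Safety is a primary endpoint (section 13.1), and section 13.4 tabulates adverse events.

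**Working it through.** The plan states no figure to reproduce. The check is a count from the calendars, followed by rough sizing.

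**1. Tests during adjuvant treatment.** Table columns were matched to weeks and checked against the drug rows: durvalumab falls on Weeks 1, 5, 9 and 13 in both tables. TSH/FT4 marks after Week 1: Cohort A, Week 9 = 1; Cohorts B and C, Weeks 5, 9 and 13 = 3. The missing weeks, 5 and 13, both have a laboratory draw in Table 10.2.

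**2. Time to the first on-treatment test** (visit windows ignored).
- From the first adjuvant dose: 9 − 1 = 8 weeks in A; 5 − 1 = 4 weeks in B and C.
- From the post-operative test (0.5 to 2 weeks after surgery), with adjuvant start 4 to 12 weeks after surgery (section 5.1):
  - A: (4 − 2) + 8 = 10 to (12 − 0.5) + 8 = 19.5 weeks.
  - B and C: (4 − 2) + 4 = 6 to (12 − 0.5) + 4 = 15.5 weeks.

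**3. Whether the combination's thyroid rate applies.** Section 2.3.5 includes hypothyroidism among events in at least 10% of patients on durvalumab plus tremelimumab ("back pain, arthralgia, hypothyroidism, asthenia, oedema peripheral"). It does not appear in the corresponding list for durvalumab alone, which ends "pyrexia, asthenia, anemia, arthralgia, peripheral edema, headache, rash, and pruritus". From tremelimumab to the first adjuvant dose is 3 + 4 = 7 to 10 + 12 = 22 weeks, or 49 to 154 days. Section 2.3.3 gives a half-life of 22.1 days, so 49/22.1 = 2.2 to 154/22.1 = 7.0 half-lives have passed. The fraction left is 0.5^2.2 ≈ 22% to 0.5^7.0 ≈ 1%. The combination rate should not be carried into the adjuvant phase. A rate below 10% is the reasonable assumption for durvalumab alone.

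**4. Patients the change could reach.** The number still to be treated is not given.
- Planned surgeries: 0.80 × 25 = 20 (section 13.2). Already resected by June 2018: 11 (section 2.6). Remaining: 20 − 11 = 9. This assumes the 11 have passed Week 13 by approval; the latest Week 13 is 12 + 12 = 24 weeks after surgery.
- Cross-check: the neoadjuvant dose precedes Week 13 by 3 + 4 + 12 = 19 to 10 + 12 + 12 = 34 weeks, or 4.4 to 7.8 months. At 1 to 2 enrolments per month (section 13.3), 4.4 to 15.7 enrolled patients would not yet have reached Week 13. At 80% surgery that is 3.5 to 12.6. The upper end needs the fastest accrual and the longest delays together, and approval at the time of the last enrolment.
- Section 13.2 expects about 25 enrolled by approval, and section 5.1 allows chemotherapy instead, so the true number may be zero.

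**5. Expected hypothyroidism.** At an assumed 5% to 10%: 9 × 0.05 = 0.45 to 9 × 0.10 = 0.9 cases, before removing patients who choose chemotherapy. Only some of these would be recognised later because of the schedule.

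**The case against.** The strongest reply is that the difference is reasonable and changes almost nothing. Cohorts B and C receive a second, newer agent after surgery, which is a plausible reason for closer laboratory monitoring. Cohort A has two scheduled tests after tremelimumab and before adjuvant treatment, plus a clinic visit, examination and adverse-event review at every dose. Table 7.7.1 calls for thyroid tests on suspicion. Asymptomatic TSH elevation needs no dose change, and isolated hypothyroidism is managed with replacement while treatment continues. No formal cohort comparison is planned.

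Most of this stands and sets the size of the point. What remains is that the reason is not written down, that the symptoms are described as non-specific, and that dosing can be affected by Grade 2 or higher endocrine events other than hypothyroidism and type 1 diabetes, which call for a hold.

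A reader might infer from the title of Table 10.2 and the at-least-10% list that Cohort A carries the higher thyroid risk in this phase. The documents do not support that: the adjuvant drug is durvalumab alone, and most tremelimumab has cleared. The absence of thyroid events from the summaries of the B and C combinations (sections 2.4.4 and 2.5.4) is no evidence of lower risk either. One summary gives no frequency list, and the other reports events only above certain cut-offs.

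**Conclusion.** The difference is real, unexplained and confined to the adjuvant phase: one on-treatment test against three, first at 8 weeks instead of 4, and none scheduled after Week 9. The supporting risk is durvalumab's own.

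This is a minor improvement. On the assumptions above, probably fewer than 10 patients and possibly none are affected, with fewer than about one expected case of hypothyroidism. Feasibility is defined by reaching surgery, and the post-surgery toxicity rule counts events of grade 3 or higher, so neither conclusion should move.

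Two further inferences should be resisted. The schedule does not breach any testing interval, because the protocol sets none outside these calendars. Nor would matching the tests make thyroid rates fully comparable: B and C have adverse-event assessments every two weeks against every four in A, and grading uses CTCAE v5.0 against v4.03.

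**What to change.** Add TSH/FT4 at Weeks 5 and 13 to Table 10.2, run on the blood already drawn at those visits, for Cohort A patients still to receive those doses. Beside the thyroid adverse-event rates, add a footnote that test schedules differed between cohorts and, after the change, within Cohort A. If no Cohort A patient remains to be treated, the footnote alone is enough.

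The cost is two extra test points per remaining patient, each a TSH and an FT4: 2 × 9 = 18 on the estimate above. No new visit or venepuncture is needed. The drawback is two test schedules within Cohort A. No cohort has a scheduled thyroid test after its last durvalumab dose, and this change leaves that as it is.
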